5.3.1 Plan for addressing confounding

This is a descriptive/exploratory and hypothesis generating study. We will acknowledge in dissemination unmeasured factors like symptom or disease severity may confound associations between the covariates and A&G and in referral following an A&G.

5.3.2 Plans for addressing missing data

We will assume that if no code for A&G or referral is entered, it did not occur. It is possible the quality of recording has improved in recent years and will discuss this as a limitation in dissemination, but we do not expect bias in recording by the covariates. Not everyone will have an ethnicity recorded, and we will use a "Not recorded" category.

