1.3 THEORETICAL FRAMEWORK

This study is underpinned by the pragmatist research paradigm. Accordingly, the study is problem centred and "real-world practice oriented" in asking "what works?" in relation to A&G to bring about change in quality care. We take a pluralist approach to answer research questions that require quantitative and qualitative lines of enquiry. Our mixed-methods evaluation has a sequential design with 4 work packages (WPs). WP1 is mixed-methods and will include a descriptive quantitative study using electronic healthcare records (EHR), specifically CPRD, and qualitative study using semi-structured in-depth PCC interviews to describe the use and experience of A&G, to identify tracer conditions and create a focus for WP2. WP2 will involve retrospective cohort studies, repeated for

NIHR 158681BADGER			
Protocol Version 2.0 18/06/2024	CPMS: 58336	IRAS No: 333799	CPRD ID: 24_004022

several tracer conditions. We will describe patient characteristics within the type of referral, with type of referral defined as A&G only; direct referral only; A&G and direct referral; no A&G and no direct referral. We will then observe the linked EHR to identify impact on quality and healthcare utilisation of A&G. WP3 runs in parallel to WP1 and WP2 and includes in-depth qualitative interviews with patients, SCSs, PCC and commissioners to understand their perspectives on the use of A&G. Interpretive description methodology¹⁹ will use clinical knowledge and the perceptions and experiences of participants to develop findings which can be applied to clinical practice, healthcare commissioning and policy development.

Reflexive thematic analysis will be used as the specific analytic strategy to identify these findings. Reflexive thematic analysis will be used allowing for familiarisation, coding, and generating and reviewing themes. Themes and subthemes will be generated iteratively by researchers independently according to commonality across the dataset, significance, and relevance to the research questions. Generated themes will be discussed with the PPIE group and stakeholders for their reflection.

WP4 uses results of WP1, WP2 and WP3 to co-design recommendations, as described below, to support best use of A&G in reducing compound pressures, whilst providing high quality care, and addressing any identified health inequalities.

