4.2.8 Exposures, outcomes and covariates

1) Advice & Guidance

We will determine coded A&G events and, where possible, the specialty linked to the A&G. When a Choose and Book referral is made through e-RS (by selecting either the satellite button for "advice and guidance" which equates to an A&G request or the "Refer/Advice" satellite button which equates to the standard or direct referral to secondary care), the referral must be saved before the activity can be completed and exited back to the clinical software system. To save the activity, a code must be entered to then move back into another part of the healthcare record. For A&G requests, the coded term is "Advice and guidance requested." We will also include in our codelist the code "Advice and guidance received" which we will use to indicate A&G if the patient does not have an "Advice and guidance requested" code within the same study time period. We will map A&G to specialty (e.g. rheumatology, neurology) and type of health condition (e.g. musculoskeletal, cardiovascular). Given A&G coded events may not routinely have the specialty recorded we will use information from direct referrals (sampled from 3 specified years - 2015, 2019, 2023 - within our study period) as the basis for mapping to specialty. We will first determine morbidity/symptom codes recorded on the date of all direct referrals (defined below) with a named specialty, or in the prior 2 weeks. We will determine which Read or SNOMED CT codes are most frequently recorded with referral to each specialty and use these to map (impute) specialties in those with an A&G event based on matching these codes to Read/SNOMED CT morbidity or symptom codes recorded on the date of A&G or in the prior 2 weeks. Where the specialty is still unknown after this mapping exercise, we will review all codes in the 2 weeks prior to or on date of A&G request and agree on specialty (guided by Read code chapter) by consensus or define as unknown if no consensus. Type of health condition will be based on specialty or morbidity/symptom code at date of A&G event.

2) Direct referral

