To derive the comparative prevalence and incidence of elective referrals, direct routine referrals will be determined using codes with a term indicating a referral and defined by consensus of study team to indicate a routine referral to a specialty (i.e. not fast track or referral with an intention to admit / emergency referral). To ascertain A&G events which result in a direct referral, we will determine

NIHR 158681BADGER			
Protocol Version 2.0 18/06/2024	CPMS: 58336	IRAS No: 333799	CPRD ID: 24_004022

referrals within 122 days (4 months) after date of an A&G request. These will be defined as i) a direct referral code defined as above and by ii) linking events in the Referrals table to the Observation table and determining duration of time between the linked observation event and the A&G request date. We will also determine referrals within 122 days (4 months) before an A&G request to see how often A&G requests follow a referral request. As a sensitivity analysis we will repeat for 365 days (12 months) either side of the A&G request date. Code lists for A&G have been derived and used in our CPRD feasibility study (FS_002830). The draft code list for direct referral has also been developed. These code lists are included in the appendix.

Covariates:

- 1) Age at date of A&G request (categorised)
- 2) Sex
- 3) Geographical region
- 4) CCG pseudonym
- 5) Ethnicity group
- 6) Deprivation (based on IMD quintiles)

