5.2.6 Planned use of linked data and benefit to patients in England

In addition to patient level Index of Multiple Deprivation (IMD) data and the CPRD Aurum Ethnicity Record as previously described, we will use Hospital Episode Statistics (HES; NHS Digital, 2022) data to access hospital admission data. The Office for National Statistics (ONS) death registration data will provide mortality records. Linkages are necessary to identify patient outcomes and healthcare utilisation.

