5.2.7 Definition of the study population

All individuals in the CPRD Aurum database, regardless of age, with a first recorded index tracer condition between 01/01/2015 to 31/12/2022 and 24 months prior registration in CPRD Aurum. We will compare outcomes for patients with a recent history of A&G to those with direct referral, stratified by tracer condition. A&G and direct referrals will be obtained from primary care records in the 24 months prior to index (first diagnosis) date. Patients with both A&G and direct referral will be classified based on whichever happened first. We will include age at index date, gender, neighbourhood deprivation, geographical region, and ethnicity, as common covariates for all analyses as well as covariates (e.g. multiple long term conditions) specific to each tracer condition. There is no comparison or control group.

The tracer conditions will be informed from the work in WP1, including interviews with PCCs, and the experiences and advice of our PPIE and Stakeholder groups.

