5.3 DATA / STATISTICAL ANALYSIS

For WP2a, the outcome for those with an A&G and/or direct referral recorded will be the time to diagnosis from the first recorded A&G or direct referral to index diagnosis date. We will calculate median (interquartile range) days to diagnosis from first recorded A&G or direct referral code and incidence rates per 1,000 person years and present with 95% confidence intervals. We will use flexible parametric survival analysis to compare A&G and direct referral on time to diagnosis. Flexible parametric survival analyses are preferred to Cox proportional hazards regression as they allow easier modelling of time-dependent effects and the ability to determine absolute risks of outcome. Exposure' will be the initial method of referral (A&G, direct referral) prior to index date. Hazard ratios will be presented as unadjusted and adjusted for covariates with 95% confidence intervals (CI).

For WP 2b, individuals with each index condition will be categorised as i) A&G only, ii) direct referral only, iii) A&G and direct referral, iv) no recorded A&G or direct referral in the 24 months before diagnosis:

- negative binomial or zero-inflated negative binomial regression will be used to estimate incidence rate ratios for the number of consultations, referrals and prescriptions in primary care, and number of outpatient appointments,
- robust Poisson regression will be used to compare A&E and unplanned admission in secondary care;
- flexible parametric survival analysis will estimate hazard ratios for mortality.

Rates or ratios will be presented as unadjusted and adjusted for covariates with 95% CI.

As part of the Study Within A Project (SWAP) (see Section 8), the impact of multimorbidity and frailty on decision to use A&G and its outcomes will be considered by including multimorbidity and frailty (defined by Charlson comorbidity index/number of prescriptions and electronic frailty index) as predictors and moderators of A&G outcome in the models.

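### In WP2b an absent code is read as no referral, so 'A&G only' and the 'no recorded' group may include patients referred without a code or by another route

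*Protocol*

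**What the plan says.** Protocol 5.3.2, which covers missing data in WP2, states: "We will assume that if no code for A&G or referral is entered, it did not occur". The same sentence appears in 4.3.2 for WP1a.

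The WP2 cohort is everyone "with a first recorded index tracer condition between 01/01/2015 to 31/12/2022 and 24 months prior registration in CPRD Aurum" (5.2.7). On exposure, the same section says: "A&G and direct referrals will be obtained from primary care records in the 24 months prior to index (first diagnosis) date". Section 5.2.8 takes the definition of direct referral from 4.2.8, where it means routine referral codes, "i.e. not fast track or referral with an intention to admit / emergency referral".

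For WP2b, 5.3 forms four groups: (i) A&G only, (ii) direct referral only, (iii) both, and "iv) no recorded A&G or direct referral in the 24 months before diagnosis". Section 1.3 words the last two differently, as "A&G and direct referral; no A&G and no direct referral".

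HES outpatient data appear in 5.2.4 as an outcome source. Section 5.2.6 gives the purpose of linkage: "Linkages are necessary to identify patient outcomes and healthcare utilisation". No check of the exposure groups against HES is described.

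Section 5.3.3 accepts that exposures may be misclassified, but expects this to be random and so not an important source of bias.

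**The concern.** In WP1a the denominator is the registered population, and most people without a code had no event. In WP2 everyone has been diagnosed with a tracer condition. The examples named are multiple sclerosis and SLE (5.2.5), and SLE, MND and endometriosis (9.1). If such diagnoses usually involve a specialist (a general assumption, not a statement in the protocol), an absent code is weaker evidence that no referral took place.

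Two mechanisms follow.

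- **Missed codes.** An uncoded routine referral moves a patient from group iii to group i, or from group ii to group iv.
- **Other routes.** Even with perfect coding, fast-track and emergency referrals are outside the definition of direct referral, within-hospital referrals would not arise in primary care, and referrals more than 24 months before diagnosis are outside the window. These patients go to group iv, or stay in group i if they also had A&G.

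At stake is the meaning of the WP2b ratios. Group i should describe care managed on advice alone. Group iv's A&E and admission ratios may partly reflect how patients entered hospital.

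**Working it through.** **The plan's own figure.** Section 5.2.5 expects about 11,000 diagnoses (7,000 × 0.20 × 8 = 11,200), 5% with A&G, and 90% power for a hazard ratio of 1.15. By Schoenfeld's formula, two-sided 5%, with every cohort member an event:

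- √(11,000 × 0.05 × 0.95) × ln 1.15 − 1.96 = 22.86 × 0.1398 − 1.96 = 1.23, so power is 0.892.
- With 11,200 events, power is 0.897.

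The figure reproduces, but it concerns the WP2a comparison and not the WP2b groups. Under the group iv assumptions below, missed referral codes barely change it: 0.889 at 95% sensitivity and 0.873 at 50%. The issue is what the groups mean, not power.

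**Misfiled share of group i.** Let r be the true share of A&G patients also directly referred, and s the share of direct referrals that are coded. A&G itself is taken as fully coded. Then

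misfiled share = r(1 − s) / [(1 − r) + r(1 − s)].

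The protocol gives no s. For r, the only planning value is 50% (4.2.5, a WP1a precision assumption). Section 1.1.2 also cites a surgical audit in which 61% of A&G requests went to outpatient clinic. The values 0.7 and 0.9 are assumptions for tracers that depend more on referral.

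| r | s = 0.95 | s = 0.90 | s = 0.80 |
|---|---|---|---|
| 0.50 | 4.8% | 9.1% | 16.7% |
| 0.61 | 7.3% | 13.5% | 23.8% |
| 0.70 | 10.4% | 18.9% | 31.8% |
| 0.90 | 31.0% | 47.4% | 64.3% |

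Example: r = 0.5, s = 0.9 gives 0.05 / (0.50 + 0.05) = 9.1%.

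**Misfiled share of group iv.** Take N = 11,000 and 5% with A&G (550). Assume a share n of all patients truly has neither A&G nor a routine referral. With n = 10% (1,100), 9,350 are truly 'direct referral only'.

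- s = 0.95: 467.5 / 1,567.5 = 30%
- s = 0.90: 935 / 2,035 = 46%
- s = 0.80: 1,870 / 2,970 = 63%

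If n = 0, the share is 100% for any s below 1. Patients who came by other routes are inside the 1,100, so these figures count uncoded routine referrals only.

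Group iv is more affected than group i when (0.95 − n)/n exceeds r/(1 − r). At r = 0.5 that means n below 47.5%. At r = 0.9 it means n below 9.5%. Hence 'probably', not 'certainly'.

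**Effect on a contrast.** Suppose the true rate ratio of group i against referred patients is 1.5 and group iii has the same rate as group ii (both assumed). The observed ratio is 1.5(1 − w) + w, where w is the misfiled share of group i. At r = 0.5 this gives 1.455 at s = 0.9, 1.417 at s = 0.8 and 1.385 at s = 0.7. These errors are random with respect to outcome, and the ratio still shrinks. If group iii differs from group ii, the contrast of i with ii can move either way.

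**The case against.** A reader might infer that groups i and iv consist mainly of patients whose referral was simply not recorded. The protocol does not support that.

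- Section 4.2.8 says of e-RS entries: "To save the activity, a code must be entered to then move back into another part of the healthcare record". It also finds referrals after A&G by linking the Referrals table to the Observation table, and 5.2.8 points WP2 to that section.
- Fast-track and emergency patients have no routine direct referral by definition, so placing them in group iv is correct under the protocol's own terms.
- Misfiled shares of 31% to 64% in group i need r = 0.9. At the 50% planning value they are 5% to 17%.
- Section 5.3 already labels group iv as 'no recorded', and nowhere names it as an unexposed reference group.
- WP2 is exploratory, its tracers are not chosen, it discloses imperfect recording, and detailed sensitivity analyses commonly go in an analysis plan.

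Most of this stands and limits the point to what may be in the groups. It does not remove it. The e-RS passage names coded terms for A&G only, the direct-referral list is a draft settled by consensus, and 1.1.2 says elective referrals usually, not always, go through e-RS. The non-occurrence rule and its defence are written into the protocol, so they are not details left for later. Two parts of that defence are also strained: 5.3.2 accepts that recording may have improved over time, yet calendar year is not a listed common covariate in 5.2.7; and 5.3.3 describes portals that differ by locality, while 5.3.2 expects no recording bias by covariates, one of which is region.

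**Conclusion.** The point holds in limited form and for WP2b only. WP2a has no group iv, because it includes only patients with a recorded A&G or direct referral. Reading an absent code as non-occurrence is not justified in a cohort defined by diagnosis. Groups i and iv may include uncoded routine referrals and patients who reached a specialist by another or earlier route.

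The size cannot be fixed from the protocol. On its 50% planning value, roughly 5% to 17% of group i would be misfiled at sensitivities of 95% to 80%, with modest dilution. The share is larger for tracers that nearly always need referral. Group iv is probably more affected (46% at 90% sensitivity if 10% truly have neither), but that rests on an assumed 10%. It would be too strong to say that the group contrasts are wrong or that these groups are mostly recording failures. The statement in 5.3.3 that random misclassification brings no significant bias is not safe as written.

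**What to change.** 1. In 5.3.2, for the WP2b groups, replace non-occurrence with 'not recorded'. Bring 1.3 into line with the 'no recorded' label in 5.3, and state that group iv will not be interpreted as patients without specialist referral.
2. In HES-linked patients, report the share of groups i and iv with an outpatient attendance in the tracer's specialty before diagnosis. Describe group iv by fast-track or emergency route where recorded.
3. Add one sensitivity analysis of the non-outpatient outcomes that excludes, or places in a separate category, group i and iv patients with such contact. Do not move them into group iii: an attendance shows specialist contact, not a GP direct referral. Leave the outpatient count on the recorded groups, so that outpatient data do not define exposure for an outpatient outcome.
4. Withdraw or qualify the statement in 5.3.3 that misclassification is random and therefore unimportant.

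The cost is small: protocol wording, one descriptive table and one sensitivity analysis. HES outpatient data are already planned, and section 5 says permissions for WP2 are still to be sought, so records from before diagnosis can be specified in that application. The check is limited to HES-linked patients, and some groups become smaller.

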5.3.3 Limitations of the study design

As above, it is possible recording of A&G and referral has improved over time.

As an observational study, there is the potential for unmeasured confounding factors to affect the findings. It will not be possible to conclude any causal relationship between variations in locality or

NIHR 158681BADGER			
Protocol Version 2.0 18/06/2024	CPMS: 58336	IRAS No: 333799	CPRD ID: 24_004022

socio-demographic characteristics for A&G versus usual referrals due to our study being both exploratory and descriptive. Misclassification of cases, exposures, and covariates is possible but expected to occur at random and so not introduce a significant degree of bias.

There may be other locality-dependent portals available for primary care clinicians to access specialist input without requiring a formal referral, such as teledermatology services and applications such as Consultant Connect, which facilitate telephone contact with the consultant/specialist and may not be coded by the GP. The consequence of this is that there may be missed episodes of A&G, but we believe this to be the minority of cases or at the more urgent end of the spectrum of clinical presentations rather than our focus on elective care.

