1 INTRODUCTION

1.1 BACKGROUND

1.1.1 Summary of the research

Whilst the use of Advice and Guidance (A&G) has been identified as a crucial part of managing NHS waiting lists, there is little evidence to understand its effectiveness in reducing compound pressures whilst maintaining a high standard of care. This multistage mixed-methods study will use large, anonymised patient data sets to explore use, benefits, and potential harms of using A&G in comparison with direct referral pathways. Parallel qualitative research will explore the use, experience, and perspectives of A&G from patients, clinicians, and commissioners, integrating findings from the quantitative research. We will provide the evidence required, an understanding of how A&G is working for whom, where, and why, to support primary care and specialist services to effectively work together to reduce compound pressures across the system, whilst promoting high quality care. The outputs of this research may serve to: a. reassure A&G users of its benefits and or b. provide recommendations to improve use to safeguard quality of care in a pressured healthcare environment.

For the purposes of this application 'Primary Care Clinician' (PCC) will be used to describe the General Practitioner (GP), Advanced/Nurse Practitioner (NP), Physician Associate (PA) or other clinician based in primary care, initiating the A&G request. 'Secondary Care Specialist' (SCS) will be used to describe the Consultant or other non-medical Clinician providing the A&G.

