The Patient Association undertook work to explore the patient's voice. Unable to engage GP practices, patients were recruited through their own newsletter and stakeholder activities. Patients (n=8) with self-reported experience of A&G primarily reported a lack of shared decision-making and partnership working and a lack of effective communication during the referral process. Improvements suggested included establishing dialogue between patients, GPs, and specialists.¹⁰

A survey of Royal College of General Practitioners clinical advisors in 2022 showed that 91.7% of GPs use A&G, with 83% finding it useful. However, concerns were identified and escalated to the CQC and NHSE. Whilst secondary care waiting lists increased following the pandemic, the number of referrals to secondary care that were rejected also increased. This rejection does not end the need for patient care and more patients and carers were felt to be being 'held' in the community, increasing the pressure on, and creating a backlog, in primary care. The RCGP reported that A&G is being used by some providers to manage waiting lists (as a tool to convert referrals to A&G or using A&G to decline referrals) to the detriment of patients and primary care.

A further survey of 366 GPs, published in Pulse Magazine in early 2023, reported that 68% felt A&G was blocking necessary referrals. 78% felt that A&G was increasing their workload, 60% felt that A&G was requiring them to work beyond their competence, and 68% reported that patients were complaining because their wish to see a specialist had been diverted. ¹² SCSs report the challenges of providing useful advice based upon limited A&G referral information, such as being asked to interpret results of investigations in the absence of relevant clinical history and/or findings and patients report being unfamiliar with referrals process and disenfranchised from A&G pathways.

Literature demonstrates that A&G can be efficient and effective in particular settings, that key aspects for service development include an understanding of suitable cases, collaborative working across the health system, consideration of resource implications, and that existing A&G services may still yield high outpatient appointments with relatively few requests ending with expedited patient journeys (e.g., investigation requests and direct advice). The evidence to date has set the scene for effective use of A&G but flagged how use varies across specialties.

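### Random misclassification is said not to cause significant bias, but in WP2a random error in the referral route pulls the A&G hazard ratio towards 1

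*Protocol*

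**What the plan says.** The sentence "Misclassification of cases, exposures, and covariates is possible but expected to occur at random and so not introduce a significant degree of bias" stands in Protocol 5.3.3 (WP2) and, in the same words, in 4.3.3 (WP1a).

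The exposure it covers in WP2a has two levels. Section 5.3 says that exposure "will be the initial method of referral (A&G, direct referral) prior to index date", and 5.2.7 adds: "Patients with both A&G and direct referral will be classified based on whichever happened first". Both routes are read from primary care codes in the 24 months before diagnosis. Section 5.3.2 takes absence of a code as absence of the event: "We will assume that if no code for A&G or referral is entered, it did not occur". Section 5.3.3 accepts that, because of other portals, "there may be missed episodes of A&G, but we believe this to be the minority of cases". The planned comparison in 5.3 is: "We will use flexible parametric survival analysis to compare A&G and direct referral on time to diagnosis".

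Section 5.2.5 sizes this on about 11,000 diagnoses, 5% with A&G, a hazard ratio of 1.15, 90% power and a 5% significance level. Section 4.2.5 expects WP1a prevalence of about 800 per 100,000 a year with limits of ±5 per 100,000.

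**The concern.** Randomness of an error does not decide whether it biases an estimate. Three errors are named in one sentence, and each acts differently:

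- Random, independent error in a two-level exposure mixes the two groups and draws the contrast towards no difference.
- Random error in a covariate means that adjustment is incomplete, so residual confounding remains.
- A missed code in a rate lowers the rate; misses do not average out.

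The first matters most in WP2a. If A&G delayed diagnosis, the hazard ratio for diagnosis would be below 1, and misclassified routes would make the delay look smaller than it is. Section 1.1.1 sets out to examine potential harms and says that the outputs may, among other uses, "reassure A&G users of its benefits". A reader who relies on 5.3.3 would not expect dilution in that direction.

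**Working it through.** **1. The plan's own power.** Inputs from 5.2.5: 7,000 a year × 20% × 8 years = 11,200, given as about 11,000; share exposed p = 0.05; hazard ratio 1.15. Every diagnosis counts as an event, and all patients are taken as belonging to one of the two groups.

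Power = Φ(|ln HR| × √(events × p(1−p)) − 1.96). Here ln 1.15 = 0.1398 and √(11,000 × 0.05 × 0.95) = 22.86, so power = Φ(3.195 − 1.96) = 89%. The Schoenfeld formula needs 11,325 events for 90%. The stated figure reproduces, for an exposure measured without error.

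**2. Effect of random error in the route.** Sensitivity (Se) and specificity (Sp) of the A&G label are assumptions; the protocol gives none.

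- Share labelled A&G: q = p·Se + (1−p)(1−Sp)
- Share of the labelled A&G group that is truly A&G: PPV = p·Se / q
- Share of the labelled direct-referral group that is truly A&G: FOR = p(1−Se) / (1−q)
- Approximate estimated ln HR = true ln HR × (PPV − FOR)

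Example, Se 80% and Sp 98%: q = 0.040 + 0.019 = 0.059; PPV = 0.040/0.059 = 0.678; FOR = 0.010/0.941 = 0.011; factor = 0.667. About a third of the labelled A&G group is wrongly labelled. A true 0.80 becomes exp(0.667 × −0.2231) = 0.86. Power for 1.15 is Φ(0.667 × 0.1398 × √(11,000 × 0.059 × 0.941) − 1.96) = Φ(0.345) = 63%.

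| Se / Sp (assumed) | PPV | Factor | True 0.80 becomes | True 1.15 becomes | Power for 1.15 |
|---|---|---|---|---|---|
| 100% / 100% | 1.00 | 1.00 | 0.80 | 1.15 | 89% |
| 90% / 99.5% | 0.90 | 0.90 | 0.82 | 1.13 | 82% |
| 80% / 99% | 0.81 | 0.80 | 0.84 | 1.12 | 72% |
| 80% / 98% | 0.68 | 0.67 | 0.86 | 1.10 | 63% |
| 80% / 100% | 1.00 | 0.99 | 0.80 | 1.15 | 81% |
| 50% / 100% | 1.00 | 0.97 | 0.80 | 1.15 | 61% |

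Simulated cohorts of 2,000,000 with a Cox fit, four runs per setting, gave means of 0.82, 0.83 and 0.86 for a true 0.80 in the second to fourth rows, and 0.80 in the last two. False A&G labels therefore drive the dilution. Missed A&G alone costs power and hardly touches the hazard ratio.

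**3. Could false A&G labels arise under this plan?** Section 5.2.7 counts A&G in the 24 months before diagnosis and does not require it to concern the tracer condition. From 4.2.5, 108,000 / 14 million = 0.77% of patients a year have A&G, or roughly 2 × 0.77% = 1.5% over 24 months (a crude doubling of a nine-year average). Against an expected 5%, unrelated A&G of that order would correspond to a specificity near 98.5%. Section 4.2.8 plans to map A&G to specialty, but 5.2.7 does not say that this will be used to exclude unrelated A&G. Section 1.1.2 also reports A&G being used by some providers "as a tool to convert referrals to A&G or using A&G to decline referrals". Neither source is measured. An unrelated A&G would also move the start of the clock, so step 2 shows the effect of label error alone and is not a forecast of the total bias.

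**4. WP1a rates.** Prevalence is 108,000 / 14 million = 771 per 100,000. The half-width is 1.96 × √(0.00771 × 0.99229 / 14,000,000) = 4.6 per 100,000, which agrees with the stated ±5. If 1% of patients with A&G are missed, the true figure is 771 / 0.99 = 779, a shift of about 8 per 100,000. That is already more than the stated limits.

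**The case against.** Several points on the other side stand.

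- **Degree.** The text denies a significant degree of bias, not all bias. A reader might infer that the protocol claims there is none; it does not.
- **Missed A&G.** The only exposure error that 5.3.3 names is missed A&G. On that error alone the WP2a hazard ratio is nearly unbiased, as the fifth and sixth rows of the table show. The A&G code is a specific term that has to be entered to save the request (4.2.8), so false labels may be few, and nothing in the document quantifies them.
- **Direction elsewhere.** One might infer that every WP2 result is pulled towards no difference. The documents do not support that. WP2b has four exposure categories, covariate error leaves residual confounding of either sign, a missed first A&G can move the start of the clock to a later direct referral, and 5.3.2 and 5.3.3 allow that recording has improved over time. None of these has an assured direction.
- **Intended use.** No conclusion of equivalence or absence of harm is planned. Section 1.1.1 offers reassurance as one possible use of the outputs, alongside recommendations to safeguard quality of care.
- **Acknowledgement.** The protocol accepts that episodes may be missed, will discuss recording quality as a limitation, and compares WP1a trends with public e-referral data. It nowhere says that the disputed sentence is its reason for not analysing misclassification.
- **Status.** WP2 is exploratory, will be designed iteratively, and could leave a bias analysis to a later document.

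These points limit the size and reach of the concern. They do not rescue the inference in the sentence, which is wrong as written, and an exploratory label does not make it right.

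**Conclusion.** The concern holds in a limited form. The inference in 4.3.3 and 5.3.3 is wrong. For the two-level WP2a exposure, independent random error attenuates the hazard ratio. At 5% A&G and the three assumed accuracy settings with false labels, a true 0.80 is estimated at about 0.82, 0.83 to 0.84 and 0.86, and power for 1.15 falls from 89% to about 82%, 72% and 63%. These sizes depend on specificity, which the protocol does not give. At 100% specificity the hazard ratio is almost unchanged and only power is lost. In WP1a a 1% miss rate exceeds the stated precision.

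The documents do not support the stronger readings that all WP2 contrasts move towards the null, that the protocol claims no bias at all, or that it plans to declare A&G harmless. What follows is narrower: a WP2a hazard ratio near 1 cannot be read on its own as evidence of no harm, and the limitations text should say so.

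**What to change.** In 4.3.3 and 5.3.3, replace the sentence with wording such as:

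*Random misclassification of initial referral route is expected to attenuate the WP2a A&G versus direct-referral contrast; missed codes will lower A&G rates; covariate error may leave residual confounding, and bias in the WP2b contrasts may go in either direction.*

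In 5.3, add a simple bias analysis that re-estimates the WP2a hazard ratio over stated ranges, for example sensitivity 70% to 100% and specificity 98% to 100%, with 100% included so that the case of missed A&G only is shown. State that a near-null WP2a hazard ratio will be interpreted in light of that range and not on its own as evidence of no harm. A single sensitivity/specificity pair does not fit the four WP2b categories, so this analysis should not be carried over to them unchanged.

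The cost is a replaced sentence, a short calculation after the main model, and wider stated uncertainty. No new data are needed.
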